8.6.4 Truth Standard

8.6.4.1 Coronary Angiography

The results of coronary angiography will be collected on-site for any subject who has the procedure within 6 months following the LUMASON administration(s). All coronary angiography images should be archived and stored on dedicated digital media according to the standard practice at the institution. Investigational sites are required to maintain the original images as a record of the study. A copy of the images shall be archived on portable digital media (e.g., digital versatile disc [DVD], magnetic optical disc [MOD], compact disc [CD], etc.) that will be forwarded to the central imaging laboratory according to the instructions in the Imaging Manual. If a subject does not undergo coronary angiography or coronary angiography is indeterminate, 6 month follow-up data will be collected to determine if the subject has CAD based on clinical information (see Section 8.6.4.2).

A fourth blinded reader will assess the coronary angiography images and provide a diagnosis of CAD. The off-site reader will be blinded to the specifics of the protocol including the patient population and the results of the echocardiographic examination, but will receive clinical information such as the medical history.

For subjects with coronary angiography as the truth standard, a subject will be diagnosed by the blinded off-site coronary angiography reader as Positive if percentage diameter stenosis of any of the vessels (RCA, LAD, LCx and LM) is $\geq 50\%$; otherwise, a subject will be considered as Negative.

8.6.4.2 6 Month Follow Up to Collect Cardiac Events

A 6 month follow up will be required for those subjects who have not had a coronary angiography or had coronary angiography with indeterminate results within the 6 months following the LUMASON administration(s).

Subjects requiring 6 month follow up will be monitored by a review of their hospital and clinic records as well as a phone call follow-up at 6 months to collect cardiac events, as defined by the incidence of: a) cardiac death; b) non-fatal myocardial infarction as defined by a greater than two fold serial elevation in serum creatine kinase-myocardial B (CK-MB) fraction levels; c) coronary revascularization; and d) documentation of the need for coronary revascularization. If a coronary angiography is performed during the 6 month follow-up, this will be collected and accepted as the truth standard for the subject. Each site will have study personnel who will be responsible for collecting phone/clinical record or coronary angiography images during the follow up period.

8.6.5 Off-Site Assessment Methodology

Digital recordings of the echocardiographic images will be blinded, randomized and assessed off-site at a core laboratory. The off-site assessment of the digital recordings will be performed by 3 independent, experienced readers, unaffiliated with the investigational sites and blinded to any clinical information for subjects enrolled in this study.

In addition, the coronary angiography images will be evaluated by a fourth blinded reader who will provide a diagnosis of CAD. This off-site reader will be blinded to the specifics of the protocol including the patient population and the results of the ultrasound examination, but will receive clinical information such as the medical history.

A separate off-site methodology document will be prepared and will contain the details regarding how the images will be anonymized, randomized and presented to the readers.

Changes to the off-site image assessment will either be reviewed and approved via a protocol amendment or described in the separate off-site image assessment document.

9 Reporting Safety Information

The investigator is responsible for the detection, documentation and reporting of adverse events.

AE collection begins when a subject signs the Informed Consent and continues through the follow-up period defined in the section 8.4.5.1 of the protocol. In addition, an investigator should report any serious AEs that occur after this time period that he/she believes may be related to the IP/IMP and/or NIMP(s).

Any untoward medical occurrence that occurs from the time of signed Informed Consent to the time immediately prior to IP/IMP administration will be tabulated in the Clinical Trial Report as a “predose event.”

9.1 Adverse Events

9.1.1 Definitions

An adverse event (AE) is any untoward medical occurrence in a subject or a clinical trial subject administered a medicinal product and which does not necessarily have to have a causal relationship with the use of the product.

Any AE that occurs after the follow-up period defined in the protocol is not required to be collected in the AE section of the CRF.

An existing condition, which is detected by the diagnostic procedure conducted to test the efficacy of an investigational contrast agent, is not considered an AE.

Symptoms or medically significant laboratory or instrumental (e.g., electrocardiographic) abnormalities of a pre-existing condition, such as cancer or other disease, should not be considered an AE. However, new symptoms and laboratory or instrumental abnormalities, as well as worsening of pre-existing ones are considered AEs.

A serious adverse event (SAE) is any untoward medical occurrence that at any dose:

- results in death,
- is life-threatening (i.e. the subject was at risk of death at the time of the event/reaction; it does not refer to an event/reaction which hypothetically might have caused death if it were more severe),
- requires in subject hospitalization or prolongation of existing hospitalization,
- results in persistent or significant disability/incapacity (where disability is defined as a permanent or substantial disruption of ability to carry out normal life functions, either reported or defined as per clinical judgment),
- is a congenital anomaly/birth defect,
- is an important medical event that may not result in death, be life-threatening, or require hospitalization but may be considered serious when, based upon appropriate medical judgment, it may jeopardize the subject and may require medical or surgical intervention to prevent any of the outcomes listed in the definition above. Examples of such events include allergic bronchospasm requiring intensive treatment in an emergency room or at home, and blood dyscrasias or convulsions that do not result in hospitalization, or development of drug dependency or drug abuse.

Any suspected transmission via a medicinal product of an infectious agent is also considered an SAE.

A non-serious AE is any AE that does not meet the criteria listed above for a SAE.

The reference safety document will be the same for the whole clinical trial.

An unexpected AE is one where the nature, severity, specificity or outcome is not consistent with the applicable product reference document.

In particular, the sponsor will determine the expectedness of the AEs reported during this clinical trial according to the following reference document(s):

LUMASON: latest version of the Investigator's Brochure (IB),

Dobutamine: latest version of PI/SPC approved in the country where the site is located which administered the NIMP to the study subject,

Atropine: latest version of PI/SPC approved in the country where the site is located which administered the NIMP to the study subject.

If an updated version of the reference safety document becomes available during the conduction of the study and before the last subject out, the Sponsor will provide the new version to all investigators. For Europe, the new version will be provided to all investigators, ECs and CAs. The new version will become the reference safety document for assessing the expectedness of AEs.

An AE with fatal outcome should be considered unexpected unless the reference safety document specifically states that the event might be associated with a fatal outcome.

When it is uncertain whether an AE is expected, the AE should be treated as unexpected.

9.1.2 Expedited Reporting a Serious Adverse Event to Sponsor

The Investigator must report all serious adverse events **within 24 hours**, by telephone or by fax, to both the Drug Safety group and the Clinical Manager of the Sponsor as listed in Table D.

A Serious Adverse Event Report (SAER, see Appendix D) must be completed by the Investigator and faxed to the Sponsor (both the Drug Safety group and the Clinical Manager) within 3 calendar days after the Investigator first became aware of the serious event. The top two copies of the completed SAER should also be sent to the Sponsor by traceable mail. The bottom copy remains on-site with the CRF.

In case of death, a comprehensive narrative report of the case should be prepared by the Investigator and sent to both the Drug Safety group and the Clinical Manager of the Sponsor by traceable mail together with the SAER, with a copy retained on-site with the CRF. If an autopsy is performed, a copy of the autopsy report should be actively sought by the Investigator and sent to the Sponsor as soon as available with a copy retained on-site with the CRF.

A follow-up SAER should be filled in by the Investigator if important follow-up information (e.g., diagnosis, outcome, causality assessment, results of specific investigations) becomes available after submission of the initial SAER. The follow-up SAER should be sent to the Sponsor in the same manner and following the same timeline as described for the initial.

If the Investigator becomes aware of any serious adverse events within the follow-up window established in the protocol following IP/IMP administration, they will be reported to both the Drug Safety group and the Clinical Manager of the Sponsor as described above.

If outside the follow-up window established in the protocol, any serious adverse events are reported to the Investigator, which he/she believes are related to the administration of the IP/IMP and/or NIMP(s), it is the Investigator's responsibility to report this serious adverse event to both the Drug Safety group and the Clinical Manager of the Sponsor. Such serious adverse events will be reported using a Serious Adverse Event Report or any other way chosen by the Investigator. Do not use the Case Report Form.

The names, telephone, fax numbers, and email address of the contact persons are given below in Table D.

Table D: Serious Adverse Event Reporting – Sponsor Contact Personnel

9.1.3 Breaking the Study Blind

This is an open-label, nonrandomized study.

9.1.4 Data Collection

The Investigator will collect adverse events through non-leading questions and examination of the subjects/subjects.

For each event, record the following information in the Adverse Event section of the Case Report Form:

- **Classification of the Event:** Classify the event as either serious or non-serious (see definitions in Section 9.1.1).
- **Description of Signs or Symptoms:** Whenever possible, record a specific diagnosis for the event. If a diagnosis cannot be made, then record each sign or symptom separately. If multiple episodes of an event occur, separated by an appropriate time interval to justify

considering the subsequent episodes as a repeat occurrence, record each episode separately on the Case Report Form. Indicate if the event is local (i.e., occurring at the site of administration). For serious AEs only: provide a detailed chronological description of the clinical course of the event(s) and of all relevant signs and symptoms.

- **Onset Date and Time:** Record the date and time the event started. If a change from predose in a laboratory test is reported as an adverse event, record the start date as the date of collection of the first lab sample that shows the change.
- **Stop Date and Time:** Record the date and time the event resolved. If a change from predose in a laboratory test is reported as an adverse event, record the stop date as the date of collection of the first postdose sample that shows a return to the predose level.
- **Intensity:**
 1. **Mild:** Event not resulting in disability/incapacity, which resolves without treatment.
 2. **Moderate:** Event not resulting in disability/incapacity, which requires treatment.
 3. **Severe:** Event resulting in temporary and/or mild disability/incapacity, which requires treatment.
- **Relationship to the IP/IMP/NIMP:** Make every effort to determine the cause of each adverse event. Classify the correlation between the IP/IMP/NIMP and the adverse event as follows:

1. **Reasonable Possibility**

The event falls into one of the two following categories:

- 1) a) The event follows a reasonable temporal sequence from administration of the IP/IMP and/or NIMP;
AND
b) The event follows a known response pattern to the IP/IMP and/or NIMP but could have been produced by any of the following features:
 - the subject's clinical state, or
 - other therapy administered, or
 - the diagnostic/interventional procedure;OR
c) The event cannot be reasonably explained by any of the following features:
 - the subject's clinical state, or
 - other therapy administered, or
 - the diagnostic/interventional procedure;OR
d) There is evidence of partial or complete disappearance of the event after withdrawal of the product (positive dechallenge).
- 2) The report of the event contains:
 - a) conflicting data
AND/OR
 - b) dubious or insufficient/poor evidence

2. **No reasonable Possibility**

The event is either a predose event or is definitely due to causes separate from the administration of the IP/IMP, i.e.,

- documented pre-existing condition
- technical and manual procedural problems
- concomitant medication and/or NIMP
- the subject's clinical state
- the event is judged as not related and does not fall under either of the categories for "reasonable possibility"
- erroneous administration of treatment

• Action Taken:

0. None

1. Change in the IP/IMP administration (including brief interruption of administration of total dose and early termination of administration, i.e., dose reduction)

2. Drug treatment required (a medication was prescribed or changed; record in the Concomitant Medication section of the Case Report Form)
 3. Non-drug treatment required (a non-drug treatment was prescribed or changed, record under “Comments” in the Adverse Event section of the Case Report Form)
 4. Hospitalization or prolonged hospitalization
 5. Diagnostic or clinical test(s) conducted (attach a copy of the results to the Case Report Form)
 6. Subject discontinued from the study
- Subject Outcome:
 1. Recovered without sequelae
 2. Recovered with sequelae (describe the sequelae under “Comments” in the Adverse Event section of the Case Report Form)
 3. Not Recovered, event on-going (follow the subject until a definite outcome can be determined. When follow-up data are collected, report follow-up information under “Comments” in the Adverse Event section of the Case Report Form; if the event is serious, fill in a follow-up Serious Adverse Event Report)
 4. Died (list primary cause of death under “Event Description” in the Adverse Event section of the Case Report Form; if available, obtain a copy of the autopsy report to the Case Report Form and send a copy to Sponsor)
 - Comments:

Provide other pertinent clinical information and observations, and the rationale for the provided causality under “Comments” in the Adverse Event section of the Case Report Form. For example, record predisposing or contributing conditions, such as previous history, concomitant diseases or medications, and/or procedural risks and explain the reasoning for attributing the event(s) to the cause chosen.

If the investigator states that there is no reasonable possibility that the event is related, he/she should provide details of an alternative explanation for the event.

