8.4.5 Safety Assessments

8.4.5.1 Adverse Events

Monitor subjects for any untoward medical occurrences from the time of signing of Informed Consent through 72 hours after the last LUMASON administration or until the subject undergoes cardiac intervention, whichever comes first. Adverse events will be collected at the 24 hour postdose visit with a follow up phone call/contact at 72 hours. Any untoward medical occurrences as a result of the administration of the NIMP(s) (dobutamine or atropine) will also be considered adverse events. However, the known response pattern resulting from the administration of NIMP(s) for the purpose used in this study will not be recorded as adverse events.

Record all untoward medical events in the Adverse Event section of the CRF as specified in Section 9. Only postdose untoward medical occurrences will be tabulated as adverse events.

All serious adverse events that occur during the study monitoring period are required to be collected regardless of the relationship to LUMASON or the NIMPs on the Serious Adverse Event Report (SAER) Form.

In addition, the investigator should report any serious adverse events that occur after the monitoring period that he/she believes may be related to the LUMASON or the NIMPs on the SAER Form.

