10.5 Safety Analysis

The safety data will be summarized for all subjects dosed. Summary tables, including clinically significant changes wherever applicable, will be presented for the following safety endpoints:

- Adverse Events
- Clinical Laboratory Evaluations
- Electrocardiograms
- Vital Signs
- Special Situations

For vital signs and ECGs, the baseline for time points at rest will be the last measurement prior to the IP/IMP administration at rest; while the baseline for time points at stress will be the measurement which is collected after administration of the pharmacologic stress agent, dobutamine, and prior to LUMASON administration at stress (CE-DSE). All adverse events will be coded by MedDRA and summarized by system organ class and preferred term, by intensity and by causal relationship to the IP/IMP. Adverse event will be summarized separately for the NIMP(s). Only those events which occur from the start of IP/IMP administration through the follow-up period defined in the protocol will be tabulated in the Clinical Trial Report as “adverse events” see Section 9.1.1.

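### Section 9.1.4 lets an adverse event due only to dobutamine or atropine be coded as related or unrelated, and neither code serves both summaries planned in 10.5

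*Combined protocol and SAP*

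**What the plan says.** Section 9.1.4 introduces the relationship item with the instruction "Classify the correlation between the IP/IMP/NIMP and the adverse event as follows". IP/IMP is LUMASON; the NIMPs are dobutamine and atropine. The item has two categories.

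- **Category 1, Reasonable Possibility.** The timing criterion is "The event follows a reasonable temporal sequence from administration of the IP/IMP and/or NIMP". One of the criteria that can accompany it is "The event follows a known response pattern to the IP/IMP and/or NIMP". Both accept either product. Conflicting or insufficient evidence also leads to category 1.
- **Category 2, No reasonable Possibility.** Apart from predose events, this is for events "definitely due to causes separate from the administration of the IP/IMP". Only LUMASON is named as the reference product, and the list of separate causes includes "concomitant medication and/or NIMP".

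Section 10.5 plans to summarize adverse events "by intensity and by causal relationship to the IP/IMP", and in the next sentence plans a separate summary for the NIMPs.

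Section 8.4.5.1 counts untoward occurrences resulting from a NIMP as adverse events, with one exception: "the known response pattern resulting from the administration of NIMP(s) for the purpose used in this study will not be recorded as adverse events". Section 9.1.4 also asks for the rationale for the chosen causality as a free-text comment, and for an alternative explanation when category 2 is chosen.

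**The concern.** The two categories do not share a reference product. Category 1 asks about LUMASON or a NIMP; category 2 asks about LUMASON and treats a NIMP as one of the other causes. An event caused by dobutamine alone can satisfy the wording of both, and the text does not say which prevails.

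This matters because of the design. Safety of LUMASON during dobutamine stress echocardiography is a stated secondary objective (section 4). The study is open-label and nonrandomized (section 6.3), so no control arm separates LUMASON events from stressor events. The second LUMASON injection follows peak dobutamine stress (section 6.5), so after that injection timing does not separate the products. For vital signs and ECGs, section 10.5 handles this by taking the stress baseline after dobutamine and before LUMASON. For adverse events the separation depends on the causality code. If sites resolve the overlap differently, identical events would be reported differently.

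**Working it through.** No figure in the plan is at issue and no arithmetic applies. The check is to list every possible attribution of an event, assign each one under the wording of 9.1.4, and see whether the result supports both summaries in 10.5.

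**Inputs.** The category 1 and category 2 definitions (9.1.4), the two planned summaries (10.5), the recording exception for known NIMP responses (8.4.5.1), and the order of dosing (6.5 and 8.5.2).

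**Step 1: assign the four attributions.**

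| Due to LUMASON? | Due to a NIMP? | Category under 9.1.4 |
|---|---|---|
| Yes | No | 1 |
| Yes | Yes | 1 |
| No | No | 2 |
| No | Yes | 1, because a NIMP link is accepted there; also 2, because a NIMP is a listed separate cause |

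Three of the four are unambiguous. The fourth, an event due only to a NIMP, is not.

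**Step 2: carry the fourth row into 10.5.**

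- Coded 1, the event enters the LUMASON-related count although LUMASON did not cause it. That table is inflated.
- Coded 2, the LUMASON-related count is right. But category 2 also holds events due to pre-existing conditions, procedural problems and other causes, so the code does not show which of its events belong to the NIMPs. The NIMP summary has no defined source rating.

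The second row adds to this: category 1 does not say whether LUMASON, a NIMP or both are suspected. So one two-level code per event cannot feed both summaries under either choice.

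**Step 3: test whether the word definitely settles the fourth row.** Suppose it acts as a tie-breaker, so that events certainly due to a NIMP go to 2 and events only possibly due to a NIMP go to 1. Category 1 would still mix possible LUMASON events with possible NIMP events. A NIMP summary built on category 1 would then omit the events most certainly caused by a NIMP. The mismatch with 10.5 remains.

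**Step 4: delimit the affected events.** Known NIMP responses never reach the item, because 8.4.5.1 does not record them. Other NIMP events do. Dobutamine starts at least 30 minutes after the rest LUMASON injection (8.5.2), so any event it causes falls after the first LUMASON dose and inside the period that 10.5 tabulates. The documents do not say how often such events are expected.

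**The case against.** The strongest defence is that the item may not be answered only once. Section 9.1.4 gives a common scale and does not say that a single answer covers all products. The separate NIMP summary in 10.5 and the product-by-product reference documents for expectedness in 9.1.1 both fit a rating per product. The case report form is not in the documents. This stands as a limit on what can be claimed: the form may already collect two ratings. It does not repair the wording, because a rating for LUMASON alone would still be given a category 1 that a NIMP link satisfies.

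Other points have partial force. The free-text rationale and the recorded onset times would let some events be reassigned, and the interval of at least 30 minutes between the rest injection and dobutamine is a LUMASON-only window. But no section says how comments would feed the tables, and onset time does not help after the stress injection. Overall incidence and the tables by system organ class and preferred term are unaffected, and serious events are collected whatever their relationship.

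Two stronger readings are tempting. A reader might infer that the LUMASON-related table cannot be produced correctly at all. The documents do not support that: if sites apply the category 2 list literally, that table is right and the NIMP summary is the one without a source. A reader might also infer that most events during stress are ambiguous. They are not. An event that could be due to either product is not definitely separate from LUMASON, so it does not qualify for category 2 and belongs in category 1.

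**Conclusion.** The concern holds in a limited form. As written, adverse events due only to dobutamine or atropine, and outside the known response pattern, can be coded either way. The LUMASON-related table in 10.5 is therefore at risk of misclassification, and the separate NIMP summary has no defined rating behind it.

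The size cannot be given. A reader might try to bound the LUMASON-related rate by assuming how many subjects have a typical dobutamine event, but events of that kind are largely excluded by 8.4.5.1, and no document gives a frequency for those that remain.

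The conclusion assumes that the relationship is collected as 9.1.4 words it. If the case report form already rates each product, what is left is a wording correction. The point deserves action before data collection because the correction is cheap and the design offers no control arm against which to check attribution.

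**What to change.** Amend section 9.1.4 to require two relationship ratings for each adverse event, one for LUMASON and one for the NIMPs. Within each rating, both categories should refer to the same product. In the LUMASON rating, drop the NIMP alternative from the Reasonable Possibility criteria and keep a NIMP only as an alternative cause under No reasonable Possibility. Word the NIMP rating the same way, with LUMASON as a possible alternative cause.

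In section 10.5, state that the table by relationship to LUMASON uses the first rating and the NIMP summary uses the second. An event attributed to both would appear in both.

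The cost is at most one extra case report form field per event and the wording change; if the form already holds both ratings, only the wording changes.
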